10.11.2.2. Corticosteroid Rescue Guidance for Non-Dermatomyositis Reasons

Non-DM reasons may include, for example, poison ivy, or asthma exacerbation.

For example, prednisone equivalent dose of 60 mg or less for 10 days or less. However, this is recommended to be avoided between Week 44 and Week 52 due to final assessments being completed. If corticosteroids for non-dermatomyositis reasons are needed within 4 weeks of the final trial visit, then efficacy assessments will be conducted at the first follow-up visit, such that it is as approximate to 4 weeks after the corticosteroid rescue.

10.11.2.3. Intra-Articular Corticosteroids

A participant who receives an intra-articular steroid injection will be allowed to continue in the treatment period of the trial. However, it is preferable to have an intra-articular corticosteroid injection >30 days before the clinical efficacy assessment visit.

A participant who receives an intra-articular corticosteroid injection within 30 days of when efficacy assessments are performed will need to complete the efficacy assessments.

10.11.2.4. Immunosuppressives/immunomodulatory Agent Rescue Medications.

A participant who requires an increase or additional non-steroid immunosuppressive/immunomodulatory agent, including prohibited medications, will be withdrawn from the treatment period and enter the follow-up period of the trial.

However, if there is a requirement for a decrease in a non-steroid immunosuppressive/immunomodulatory agent for a safety or a tolerability issue, then this may be allowed after a discussion with the medical monitor and should be documented.

10.11.2.5. NSAIDs and Analgesics

The dose and the frequency of NSAIDs, acetaminophen, aspirin and other analgesic or pruritis medication is recommended to remain stable throughout the clinical trial.

Addition of a new or an increase in the dose of NSAIDs, aspirin or pruritis medications are allowed, but their use is recommended to be minimized as much as possible and documented, because they may potentially affect efficacy parameters (eg, the skeletal disease activity VAS, arthritis assessment and gastrointestinal disease activity VAS for the MDAAT and thus is recommended to be used judiciously.

Participants taking additional frequency/dose of NSAIDS/analgesics, including topical NSAIDS (that were not being used at screening/baseline), are recommended to not take the additional dose of these medications within 24 hours prior to clinical assessment visits.

Acetaminophen is primarily an analgesic and lacks the anti-inflammatory properties of other NSAIDS. The use of acetaminophen is recommended, when possible, to treat non-dermatomyositis related conditions, in the absence of a pre-existing hepatic function deficiency.

10.12. Appendix 12: Abbreviations

The following is a list of abbreviations that may be used in the protocol.

Abbreviation	Term
ADA	anti-drug antibody
ADL	activities of daily living
AE	adverse event
ALT	alanine aminotransferase
ANCOVA	analysis of covariance
anti-IFNAR1	interferon-alpha/beta receptor alpha
anti-IFN α	anti-interferon alpha
AST	aspartate aminotransferase
AUC	area under the curve
AV	atriaventricular
AZA	Azathioprine
β	beta
β -hCG	beta-human chorionic gonadotropin
BP	blood pressure
BUN	Blood Urea Nitrogen
C-CASA	Columbia Classification Algorithm of Suicide Assessment
C_{max}	maximum (or peak) serum concentration
CDASI	Cutaneous Dermatomyositis Disease Area and Severity Index
CFR	Code of Federal Regulations
CI	confidence interval
CIOMS	Council for International Organizations of Medical Sciences
CK	Creatinine Kinase
CL	Chloride
CL/F	Clearance of drug from plasma
CK-MB	Creatinine Kinase MB enzyme
COVID-19	Corona Virus Disease 2019
CRF	case report form
CRO	Clinical Research Organization
CSM	core set measure
CSR	clinical study report
C-SSRS	Columbia-Suicide Severity Rating Scale
CT	clinical trial
CV	cardiovascular
CYP	cytochrome P450 enzymes
DDI	drug-drug interaction
DILI	drug-induced liver injury
DLQI	Dermatology and Life Quality Index
DM	dermatomyositis

Abbreviation	Term
DMARDs	disease-modifying antirheumatic drugs
DMC	Data monitoring committee
DNA	deoxyribonucleic acid
EC	ethics committee
ECC	Emergency contact card
ECG	electrocardiogram
EDB	Exposure during breastfeeding
EDP	exposure during pregnancy
eGFR	Estimated glomerular filtration rate
EMA	European medicines agency
EOS	end of study
ePPND	enhanced pre and postnatal development
EQ-5D-5L & EQ-VAS	European Quality of Life, 5 Dimension, 5 Level Scale and Visual Analogue Scale
EU	European Union
ET	early termination
EudraCT	European Union Drug Regulating Authorities Clinical Trials Database
FAS	Full analysis set
FDA	Food and Drug Administration
FIH	first in human
FSH	follicle-stimulating hormone
GCP	Good Clinical Practice
GGT	gamma-glutamyl transferase
GLP	good laboratory practice
HAQ-DI	Health Assessment Questionnaire and Disease Index
HEENT	head, eyes, ears, nose and throat
HR	heart rate
HRT	Hormone replacement therapy
hsCRP	high-sensitivity C-reactive protein
HTA	Health technology assessment
IA	Interim Analyses
IB	Investigator's Brochure
ICD	informed consent document
ICH	International Conference on Harmonisation
ID	identification
IFN β	interferon beta
IFNAR	interferon- α/β receptor
Ig	immunoglobulin
IgG1	immunoglobulin G1
IL-6	interleukin 6
IM	intramuscular

Abbreviation	Term
IMACS	International Myositis Assessment & Clinical Studies
IMP	investigational medicinal product
IND	investigational new drug application
INF	interferon
INR	international normalized ratio
IP	investigational product
IPAL	Investigational product accountability log
IRB	institutional review board
IRT	interactive response technology
ISR	injection site reaction
IV	intravenous
IVIG	intravenous immunoglobulin
JAK	Janus kinase
LANCOVA	longitudinal analysis of covariance
LDH	lactate dehydrogenase
LFT	liver function test
LSLV	last subject last visit
MAD	multiple ascending dose
MCS	multiple chemical sensitivity
MDAAT	Myositis Disease Activity Assessment Tool
MDI	Muscle Disease Index
MMF	Mycophenolate mofetil
MMT-8	Manual Muscle Testing-8 designated muscle groups
6-MP	Mercaptopurine
MTX	Methotrexate
N/A	not applicable
NAb	neutralizing anti-body
NIMP	Non investigational medicinal products
NSAID	Non-steroidal anti-inflammatory drugs
PCS	physical component scores
PD	Pharmacodynamics
PE	physical examination
PhGA	physician global assessment
PI	principal investigator
PK	pharmacokinetics
PR interval	period, in milliseconds, that extends from beginning of P wave until beginning of QRS complex
PRO	patient reported outcome
PT	prothrombin time
PtGA	Patient global assessment
PTT	partial thromboplastin time
PVC	Premature ventricular contractions

Abbreviation	Term
QoL	quality of life
QRS complex	combination of the Q wave, R wave and S wave
QT interval	measure between Q wave and T wave
QTcF	QT interval calculated by Fridericia's formula
Q4W	every 4 weeks
R _{ac}	Accumulation ratio
RBC	Red blood cell
RNA	ribonucleic acid
SAD	single ascending dose
SAE	serious adverse event
SAP	statistical analysis plan
SARS-CoV-2	severe acute respiratory syndrome coronavirus 2
SC	subcutaneous
Scr	Serum Creatinine
SF-36	The Short Form (36) Health Survey
SoA	schedule of assessments
SLE	systemic lupus erythematosus
SOC	system organ class
SOP	standard operating procedure
SRSD	single reference safety document
SUSARs	Suspected Unexpected Serious Adverse Reaction
T _{max}	time drug is present at maximum concentration in serum
TBili	total bilirubin
TEAE	treatment-emergent adverse event
TIS	Total Improvement Score
TNF	tumor necrosis factor
T _{1/2}	half-life
ULN	upper limit of normal
Upr:Ucr	Urine protein: Urine creatinine
US	United States
VAS	visual analog scale
V _{ss}	volume at steady state
V _z /F	volume of distribution at pseudo-distribution equilibrium/fraction absorbed
WBC	white blood cell
WOCBP	women of child bearing potential

## 1. VERSION HISTORY

**Table 1. Summary of Changes**

Version/ Date	Associated Protocol Amendment	Rationale	Specific Changes
1 30 Nov 2021	Original 3 Sept 2021	N/A	N/A

NOTE: *Italicized* text within this document has been taken verbatim from the Protocol.

## 2. INTRODUCTION

This statistical analysis plan (SAP) provides the detailed methodology for summary and statistical analyses of the data collected in Study C0251008. This document may modify the plans outlined in the protocol; however, any major modifications of the primary endpoint definition or its analysis will also be reflected in a protocol amendment.

### 2.1. Study Objectives, Endpoints, and Estimands

**Table 2. List of Study Objectives, Estimands, and Endpoints**

Objectives	Endpoints	Estimands
Primary:	Primary:	Primary:

 
To evaluate the long-term safety and tolerability of PF-06823859.
 
	
 
Incidence of AEs, laboratory abnormalities, changes in vital signs, and ECG findings.
 
	
 
There are no defined estimands for safety and tolerability endpoints; these will be analyzed using Pfizer data standards, as applicable.
 

Secondary:	Secondary:	Secondary:

 
To evaluate the long-term efficacy of PF-06823859 in adult participants with moderate to severe DM.
 
	
 
Change from baseline in CDASI activity score at Week 52.
 
	
 
E1: This estimand uses a hypothetical estimand strategy (ICH E9 addendum) estimating the mean effect of PF-06823859 in the absence of intercurrent events (study withdrawal). This is the mean change from baseline to Week 52 CDASI activity score for all randomized and dosed participants with non-missing baseline score in the (a) Skin Analysis Set and (b) Muscle
 

	
 
Absolute values and change from baseline of CDASI activity and CDASI damage scores at all scheduled timepoints.
 
TIS score at Week 52 and at intermediate scheduled timepoints for participants who entered from Stage 3 of Protocol C0251002.
 
Change from baseline in the CSMs of the TIS including PhGA, PtGA, MMT-8, HAQ-DI, muscle enzymes, and MDAAT at Week 52 and at intermediate scheduled timepoints.
 
	
Analysis Set (see details in Section 4).
 
 
These additional CDASI endpoints will be analyzed using E1 at all scheduled timepoints.
 
E2: This estimand uses a hypothetical estimand strategy (ICH E9 addendum) estimating the mean effect of PF-06823859 in the absence of intercurrent events (study withdrawal). This is the mean TIS at Week 52 for all randomized and dosed participants included with non-missing baseline score in the Muscle Analysis Set (see details in Section 4).
 
The endpoints for the CSM of the TIS will be analyzed using E2 at Week 52 and all intermediate scheduled timepoints.
 

Tertiary/Exploratory:	Tertiary/Exploratory:	Tertiary/Exploratory:

 
To characterize pharmacokinetics (PK) of PF-06823859.
 
To characterize pharmacodynamics (PD) effects of PF-06823859.
 
To evaluate immunogenicity of PF-06823859.
 
To evaluate the effect of PF-06823859 on suicidality assessment over time in participants with active DM.
 
To evaluate the effect of PF-06823859 on SF-36
 
	
 
Plasma concentrations of PF-06823859.
 
Absolute values and change from baseline in the values of selected biomarkers at all scheduled time points.
 
Incidence of ADA and NAb.
 
Absolute values and change from baseline values of Columbia-Suicide Severity
 
	
 
Not applicable.
 

(v2 acute) and EQ-5D-5L PROs.	Rating Scale (C-SSRS) at all scheduled time points.  

Absolute values and change from baseline in the values of PROs including SF-36 (v2 acute) and EQ-5D-5L at all scheduled timepoints.

	
--------------------------------------	--	--

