6.8.3. Corticosteroids

Please refer to [Appendix 11, Section 10.11](#).

The decision for increasing or tapering steroids is entirely up to the study investigator, and any change in the steroid dose should be recorded on the concomitant medication page.

All concomitant treatments including corticosteroids or equivalent taken during the study must be recorded in study records with indication for use, total daily dose, and start and stop dates of administration.

Oral corticosteroids taken by the participants during the study will be captured on a separate CRF. The CRF page will capture the name of the corticosteroid taken, indication for use, total daily dose, route of administration, and start date and stop dates of administration.

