10.11. Appendix 11: Corticosteroid Suggested Taper and Rescue Guidance

10.11.1. Corticosteroid Suggested Taper

The following protocol recommended corticosteroid taper is provided as a guide only. Corticosteroid tapering is ultimately based upon investigator discretion.

The protocol recommended corticosteroid taper is suggested to be started after Week 4 of the C0251008 study. It is also suggested that no corticosteroid tapering occurs between Week 44 and Week 52 due to final assessments being completed. All doses are in prednisone equivalent.

Recommended Oral Prednisone Taper (all doses are approximate as these are examples only):

- **Prednisone dose of 15-20 mg:**
 - Decrease by 2.5 mg every 4 weeks. If starting dose is 19 or 18 mg, then first decrease will be to 17.5 mg a day. If starting dose is 16 or 17 mg, then first decrease will be to 15 mg a day.
- **Prednisone dose of 10-15 mg**
 - Decrease by 2.5 mg every 4 weeks. If starting dose is 13 or 14 mg, then first decrease will be to 12.5 mg. If starting dose is 11 or 12 mg, then first decrease will be to 10 mg.
- **Prednisone dose of 5-10 mg:**
 - Decrease by 1 mg every 2 weeks. If starting dose is 7.5 mg, then first decrease will be to 7 mg.
- **Prednisone dose of 5 mg or less:**
 - No taper is recommended, but prednisone dose can be tapered as per the investigator.

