10.11.2. Corticosteroid Rescue Guidance

10.11.2.1. Oral or Intramuscular Corticosteroid Rescue Recommended Guidance for Dermatomyositis Related Reasons

Systemic corticosteroids may be increased as clinically required; however, are suggested to remain within the following stipulations as a guidance.

Recommended Oral or Intramuscular corticosteroid rescue therapy:

- Two of the following options, or the same option used twice are allowed at any time, except between Week 44 and Week 52 due to final assessments being completed.
- Each event of corticosteroid rescue is recommended to be recorded on the concomitant medication pages (All doses are approximate as these are examples only):
 1. Increase in oral corticosteroid dose up to the participant's baseline dose (dose at Day 1). Consideration can then be given to following the protocol driven corticosteroid recommended taper.
 2. Increase in oral corticosteroid dose up to 20 mg of prednisone equivalent per day. Consideration can then be given to following the protocol driven corticosteroid recommended taper.
 3. Oral corticosteroid taper of 20 mg prednisone equivalent per day of over 1 month can be given on top of the baseline corticosteroid dose.

Recommended taper on top of the baseline dose as follows: 20 mg prednisone equivalent per day for 1 week, then 15 mg per day for 1 week, then 10 mg per day for 1 week, then 5 mg per day for 1 week, then back to baseline corticosteroid dose. Consideration can then be given to following the protocol driven corticosteroid recommended taper.

4. An intramuscular injection of approximately 40 mg Depo-Medrol (methylprednisolone acetate suspension [50 mg prednisone equivalent]) as an example. Consideration can then be given to following the protocol driven corticosteroid recommended taper.

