### 2.1.2. Secondary Estimand(s)

*Two estimands are defined for this study. Estimand 1 (E1) will support specified CDASI assessments at specified timepoints for participants in the Skin Analysis Set and Muscle Analysis Set separately. Estimand 2 (E2) will support TIS and CSM assessments at specified timepoints for participants in the Muscle Analysis Set.*

*E1 will be the population average effect of PF-06823859 on CFB in CDASI activity score at Week 52 for all randomized and dosed participants with non-missing baseline in a specified analysis set (Skin or Muscle Analysis Set) in the absence of dropout. Measurements taken after a participant withdraws from treatment will be censored and treated as missing data. The population-based estimate for the effect of PF-06823859 will be the mean CFB in CDASI-activity score at Week 52.*

*E1 will also be applied to each combination of the following endpoints, timepoints, and analysis sets:*

- Endpoints: Change from baseline and absolute values of CDASI activity score and CDASI damage score;*
- Timepoints: Week 52 and all scheduled intermediate timepoints;*
- Analysis sets: Skin Analysis Set and Muscle Analysis Set.*

*E2 will be the population average estimate for the effect of PF-06823859 on TIS at Week 52 for all randomized and dosed participants with non-missing baseline in the Stage 3 Muscle Analysis Set in the absence of dropouts. Measurements taken after a participant withdraws from treatment will be censored and treated as missing data. The population-based estimate for the effect of PF-06823859 will be the mean TIS at Week 52.*

*E2 will also be applied to each combination of the following endpoints and timepoints in the Stage 3 Analysis Set:*

[figure not shown]
- *Endpoints: TIS and change from baseline in each of the CSM of the TIS.*
- *Timepoints: Week 52 and all scheduled intermediate timepoints.*

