#### 6.1.1.1. Sensitivity/Supplementary Analyses

### 6.2. Secondary Endpoint(s)

#### 6.2.1. CDASI Activity and Damage Scores

##### 6.2.1.1. Main Analysis

- Estimand strategy: E1.

- Analysis sets: Skin Analysis Set and Muscle Analysis Set.
- Analysis methodology: Each CDASI endpoint (including CFB CDASI activity score, CFB CDASI damage score, absolute value of CDASI activity score, and absolute value of CDASI damage score) will be analyzed using LANCOVA including data from baseline to Week 52 with week as a fixed effect and baseline score as a covariate and an unstructured covariance matrix ([Section 5.2.1](#)).
- Intercurrent events and missing data: Data after study drug discontinuation will be excluded; intermediate missing values will not be imputed.
- The sample size, mean, standard deviation, median, minimum, and maximum at the baseline and postbaseline visits for observed CDASI scores and change from baseline CDASI scores will be presented for each cohort for each CDASI endpoint.
- For each CDASI endpoint, the least-squares (LS) means and the 90% confidence interval for the LS means will be presented and plotted for all postbaseline visits.

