### **6.5.4. Concomitant Medications and Nondrug Treatments**

All concomitant medication(s) as well as non-drug treatment(s) will be provided in the listings. These will be listed for each cohort and cohort will be indicated. A separate listing may be provided for DM-related prior and concomitant medications.

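### E1 and E2 set no strategy for permitted oral steroid rescue, so CDASI, TIS and core set scores taken on study drug at a steroid dose above the Day 1 dose are reported as the effect of PF-06823859

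*SAP*

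**What the plan says.** **Estimands and exclusion rule.** SAP Table 2 gives E1 and E2 a hypothetical strategy, "estimating the mean effect of PF-06823859 in the absence of intercurrent events (study withdrawal" being the only event listed. SAP 2.1.2 gives the working rule: "Measurements taken after a participant withdraws from treatment will be censored and treated as missing data". The CDASI main analysis (SAP 6.2.1.1) repeats it: "Data after study drug discontinuation will be excluded; intermediate missing values will not be imputed". The TIS and core set measure (CSM) analyses (SAP 6.2.2.1, 6.2.3.1) do the same. The applied rule is wider than the label in Table 2, because Protocol 7.1 keeps participants who stop study drug in the study. Neither version covers someone who is rescued and keeps dosing.

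**Rescue on treatment.** For dermatomyositis, Protocol 10.11.2.1 says: "Two of the following options, or the same option used twice are allowed at any time, except between Week 44 and Week 52". Option 1 restores the Day 1 oral dose. Option 2 is: "Increase in oral corticosteroid dose up to 20 mg of prednisone equivalent per day". Option 3 is a four-week course on top of the baseline dose, and option 4 is an intramuscular injection. On tapering, Protocol 10.11.1 adds: "It is also suggested that no corticosteroid tapering occurs between Week 44 and Week 52 due to final assessments being completed".

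**Reporting.** SAP 6.5.4 states: "All concomitant medication(s) as well as non-drug treatment(s) will be provided in the listings", with an optional separate listing for DM-related medication. Mean steroid use appears only among the baseline summaries (SAP 6.5.1). The supportive analyses in SAP 6.2.1.2, 6.2.2.2 and 6.2.3.2 do not mention rescue, and SAP 6.4 plans no subset analysis. The data will exist, since Protocol 6.8.3 says: "Oral corticosteroids taken by the participants during the study will be captured on a separate CRF".

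**The concern.** The estimand is worded as the effect of one drug. Take a participant whose disease worsens on PF-06823859, whose prednisone is raised above the Day 1 dose, and who then improves. That score enters the mean and can count as a TIS response at 20, 40 or 60. There is no control arm in which the same rescue would occur, and no planned summary table shows how often it happens.

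The protocol itself treats steroids as able to move the scores. It discourages rescue and taper in Weeks 44–52 because of the final assessments. It moves the final efficacy assessment to the first follow-up visit after late steroid use for other conditions (10.11.2.2). It also prefers intra-articular injections to be more than 30 days before an efficacy visit (10.11.2.3).

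What is at stake is how the secondary efficacy results are read. The primary safety analysis is not touched.

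**Working it through.** **Step 1. Trace each route to the exclusion rule.**

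| Route | Protocol sections | Scores in E1/E2? |
|---|---|---|
| Option 1, oral, up to the Day 1 dose | 10.11.2.1 | Kept, but steroid exposure is no higher than at the baseline used for change and TIS |
| Option 2, muscle cohort | 10.11.2.1; 20 mg/day limit in Table 4 | Kept; above the Day 1 dose if that dose was below 20 mg |
| Option 2 up to 20 mg, skin cohort | 10.11.2.1 against the 15 mg/day limit in 6.1.1.2 and Table 4 | Undetermined above 15 mg |
| Option 3, 20 mg on top of baseline | 10.11.2.1 against Table 4 | Undetermined in the skin cohort, and in the muscle cohort for anyone with a background dose |
| Option 4, intramuscular | 10.11.2.1 against 6.8.4 and Table 4 | Undetermined |
| Intra-articular | 10.11.2.3 against Table 4 | Undetermined |
| New or increased IVIG | 8.4.3 and Table 4 against 10.11.2.4 | Undetermined |
| Oral above 100 mg/day, or pulse IV | 6.8.4 | Treatment ends; later scores excluded |
| Severe flare needing more than is permitted | 6.8.3.1 | Treatment ends; later scores excluded |
| Added or increased non-steroid immunosuppressant | 10.11.2.4 | Treatment ends; later scores excluded |

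On-treatment oral rescue above the Day 1 dose is therefore kept, with option 2 in the muscle cohort as the case free of conflict.

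**Step 2. Does the Week 44–52 gap protect Week 52?** Only in part.

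- Option 2 started just before Week 44: the dose has no fixed end, a later taper is only to be considered, and tapering is discouraged until Week 52. The participant can be on 20 mg/day at the Week 52 assessment.
- Option 3 started just before Week 44: the 20/15/10/5 mg weekly steps finish by Week 48, leaving nothing above baseline at Week 52.
- Weeks 12, 24 and 36: no gap applies, yet SAP 2.1.2 applies E1 and E2 at every scheduled timepoint.

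**Step 3. Size.** The documents give no rescue rate and no rescue effect, so there is no planned figure to reproduce. As an illustration:

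shift in cohort mean = f × b

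where f is the share scored on rescue and b is the CDASI points due to rescue. Both are assumptions.

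| f | b = 5 | b = 10 |
|---|---|---|
| 10% | 0.5 | 1.0 |
| 20% | 1.0 | 2.0 |
| 30% | 1.5 | 3.0 |

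For scale, the 90% half-width of a single mean is t(0.95, n−1) × SD/√n. With the Stage 1 active-arm SD of 9.14 (Protocol 4.3) and assumed cohort sizes, it is 5.30 (n = 10), 4.16 (n = 15) and 3.53 (n = 20). The illustrated shift lies inside the half-width in each case: at n = 15 it runs from 0.5/4.16 = 12% to 3.0/4.16 = 72% of it. That SD describes Week 12 change from the parent study's baseline and may not fit change from the extension baseline.

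For the TIS response rates with an assumed 15 in the cohort, each rescued responder adds 1/15 = 6.7 percentage points.

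**Step 4. Direction.** Rescue above the Day 1 dose pushes scores towards benefit. Protocol 10.11.1 suggests tapering from after Week 4, and a dose below the Day 1 dose at a visit can push scores against the drug. Table 4 instead refers to tapering as permitted after Week 52, so this also needs reconciling. The net direction cannot be derived from the documents.

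**The case against.** The best case for leaving the plan alone has four parts.

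- The endpoints are secondary, uncontrolled and descriptive, with no hypothesis tests or p-values.
- Keeping on-treatment scores regardless of rescue is a legitimate choice.
- The heaviest rescue already ends treatment, so its later scores are excluded.
- With about 30 participants, a listing shows every medication.

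The first three stand, and they confine the point to interpretation and to participants who stay on drug. They do not settle it: if rescue data are kept, the estimand should say so, and it now attributes the result to the drug alone. The listing does not replace a summary of dose by visit, and it leaves the label unchanged.

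A reader might infer more than the documents support:

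- *That scores on newly added IVIG are kept.* Table 4 permits IVIG without a stable-dose or no-new-start condition. But 10.11.2.4 ends treatment for anyone needing an additional immunomodulator, and no section says whether IVIG is one. Sections 6.1.1.2 and 8.4.3 also speak of participants already receiving it.
- *That every rescue option stays in the analysis.* The intramuscular, intra-articular and skin-cohort passages contradict each other.
- *That option 1 inflates the result.* It only restores the Day 1 dose.
- *That Week 52 has no protection, or that the bias always favours the drug.* Steps 2 and 4 show otherwise.

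**Conclusion.** The point holds for permitted oral steroid rescue above the Day 1 dose while study drug continues. E1 and E2 state no strategy for it, the models keep the scores, and the result is called the mean effect of PF-06823859 when it is drug plus permitted rescue. The firm example is option 2 in the muscle cohort, for a participant whose Day 1 dose was below 20 mg. It can reach Week 52, and the earlier efficacy visits are open to it.

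The size is unknown. The 0.5–3.0 CDASI points and the 6.7 percentage points per rescued responder rest wholly on assumed rescue rates, rescue effects and cohort size. Tapering may offset some of it. Data after new or increased IVIG, intramuscular or intra-articular steroid, or rescue above the skin-cohort limit cannot be classified until the protocol passages agree.

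**What to change.** First reconcile the protocol passages on IVIG changes (8.4.3 and Table 4 with 10.11.2.4), intramuscular steroid (6.8.4 and Table 4 with 10.11.2.1), intra-articular steroid (Table 4 with 10.11.2.3), rescue above the skin-cohort limit (6.1.1.2 and Table 4 with 10.11.2.1) and taper timing (Table 4 with 10.11.1). Which rule is right is not a statistical question.

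Then, in SAP 2.1.2 and 6.2.1–6.2.3:

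1. Name permitted on-treatment steroid rescue for dermatomyositis, and any IVIG change that the reconciled protocol allows on treatment, as intercurrent events. State that the main analysis keeps these data and so estimates PF-06823859 plus permitted rescue.
2. Add to the TIS ≥20/40/60 table a supportive row that counts a participant as a non-responder at visits where the steroid dose is above the Day 1 dose, or within 4 weeks after such rescue. Four weeks is the interval used in Protocol 10.11.2.2.
3. Repeat the CDASI, TIS and CSM models with those same assessments set to missing. This relies on the missing-at-random assumption in SAP 5.3, which should be said beside the result.
4. Tabulate by visit and cohort the number rescued and the daily prednisone-equivalent dose. This shows taper as well as rescue.

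The cost is SAP wording and a few supplementary outputs. The oral steroid dose and dates are already on their own CRF. The main estimates do not change. The supportive response rates will be less favourable if rescued responders occur, and the model in item 3 loses some observations in small cohorts.
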